### 5.2.1 Scientific Rationale for Study Design

A double-blind, two-arm, parallel-group design represents an ideal setting to provide comparative long-term immunogenicity and safety data for the new [CCI](#) formulation versus Humira®.

Regulatory agencies are aware of the difficulty to power for safety and immunogenicity.

According to EMA “the investigation of safety is a multidimensional problem. Although some specific adverse effects can usually be anticipated and specifically monitored for any drug, the range of possible adverse effects is very large, and new and unforeseeable effects are always possible. Further, an adverse event (AE) experienced after a protocol violation, such as use of an excluded medication, may introduce a bias. This background underlies the statistical difficulties associated with the analytical evaluation of safety and tolerability of drugs, and means that conclusive information from confirmatory clinical trials is the exception rather than the rule. In most trials the safety implications are best addressed by applying descriptive statistical methods to the data, supplemented by calculation of confidence intervals wherever this aids interpretation.” [\(20\)](#).

Concerning immunogenicity assessment, regulatory agencies currently prefer to focus on a comprehensive, yet descriptive, presentation and correlation of the immunogenicity data generated in clinical studies [\(21, 22, 23, 24, 25\)](#).

According to regulatory guidance and literature, data captured in the study should allow exploration of the possible correlation of the immunogenicity assessment to PK (eg,  $C_{trough}$ ), safety (eg, injection site reactions), and/or efficacy (eg, reduced or loss of clinical response) [\(26, 27\)](#). In addition, the kinetics of an immune response (time to anti-drug antibodies [ADA], titer over time, persistent or transient ADA) observed will be used to compare the proposed biosimilar with the reference product to contribute to the totality of evidence and to the biosimilarity claim.

For all these reasons, the proposed study cannot be powered to demonstrate equivalence in safety and immunogenicity.

In this study, RA patients must have active disease, and be inadequate responders to methotrexate (MTX). The patients will continue to use MTX at a stable dose in combination with adalimumab

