7.1 Sample Size

According to the European Medicine Agency (EMA) recommendation (EMA/CHMP/SAWP/200743/2016), a total of 100 patients/arm should be adequate for a study primarily focusing on safety. To account for drop outs, this descriptive study will include 260 randomized patients in total (130/arm) in order to ensure 200 subjects are in the study at Week 52. In fact, based on averaged originator's dropout rates at Week 52, a 20% rate of drop-out overall is included in the sample size calculation (1, 2, 3). This sample size will permit an informative assessment of the

occurrence of most common AESIs (> 1/10) such as injection site reactions and rash with a precision of 12.0% and 9.0% for the AESI incidence of 26.0% and 11.0% respectively (0).

A subset of 60 patients (30 per treatment arm) will be randomly selected across all sites to participate in population PK analysis.

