15.2.2 Other Secondary Efficacy Endpoint Analyses

Other secondary efficacy endpoints will be summarized descriptively according to the type of outcome. ACR50 at Week 12 will be presented by subgroups as defined in Section 10.2.6 for ITT analysis set, but there will be no breakdown by subgroup for the remaining efficacy endpoints. All analyses will be carried out on both the ITT and the PP analysis sets.

15.2.2.1 ACR20 at Weeks 2, 4, 8, 24, and 52

These endpoints will be analyzed as per the key secondary endpoint (see Section 15.2.1).

Additionally, time to achieve ACR20 response will be will be measured from Trial Day 1. The subjects who did not achieve ACR20 before or at Week 52 will be censored at the date of their last ACR assessment prior to or at Week 52. Subjects who did not have any post-baseline ACR assessment will be censored at time = 1 day.

Results will be summarized by means of Kaplan-Meier curves together with a summary of associated statistics (median, confidence interval) and the number of subjects under risk on the ITT analysis set.

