15.3.2 Immunogenicity Analysis

Immunogenicity data will be summarized by treatment arm for the SAF analysis set. Overall ADA status (negative or positive, where positive is defined as at least one positive result post-dose) will be summarized as well as ADA titers and presence or absence of neutralizing antibodies.

Time to positive ADA status, calculated from Trial Day 1, will also be analyzed. Subjects who discontinued the study or were lost to follow-up, or had not reached the endpoint of interest at the time of analysis, will be censored at the date of last sample collection. Results will be summarized by means of Kaplan-Meier curves together with a summary of associated statistics (median, 95% confidence interval) and the number of subjects under risk.

Summary statistics will be presented for the actual titer values, by treatment arm and visit up to Week 52. Boxplots will be produced to present the ADA titer results graphically. The boxplots will present Q1, Q3, median, minimum and maximum.

The number and percentage of ADA positive and NAb positive subjects will be presented for each visit up to Week 52.

The analysis exploring the correlation between ADA and efficacy, PK and safety will be described in Sections 15.3.2.1, 15.3.3.1, and 16.6 respectively.

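### Read literally, the SAP's censoring rule for time to ADA discards positive results already observed in subjects who later leave the study, which biases the Kaplan-Meier ADA incidence downward

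*SAP*

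**What the plan says.** SAP 15.3.2 plans a Kaplan-Meier analysis of time to positive ADA status from Trial Day 1, in the safety analysis set. Its censoring sentence covers "Subjects who discontinued the study or were lost to follow-up, or had not reached the endpoint of interest at the time of analysis", who "will be censored at the date of last sample collection".

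The first paragraph of the same section defines overall ADA status: "positive is defined as at least one positive result post-dose". Completing the study is not a condition.

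The SAP's rule for its time-to-ACR20 analysis (15.2.2.1) is worded differently: "The subjects who did not achieve ACR20 before or at Week 52 will be censored at the date of their last ACR assessment".

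Protocol 5.2.1 names the immune-response kinetics to be used in comparing the two products: "time to anti-drug antibodies [ADA], titer over time, persistent or transient ADA". Protocol 8.5.3.5 lists time to ADA among the immunogenicity summaries.

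On dropout, SAP 7.1 says that "a 20% rate of drop-out overall is included in the sample size calculation", with the sample size set "in order to ensure 200 subjects are in the study at Week 52".

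**The concern.** The censoring sentence joins three groups by 'or', and only the third is tied to not having had the event. That third group alone already contains every subject without a positive sample. Taken at face value, then, the first two groups can add only subjects who did have a positive result before leaving.

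A subject first positive at Week 4 who leaves at Week 20 would be ADA positive in the status table and censored in the Kaplan-Meier curve. Whether the observed event counts would depend on what happened to the subject afterwards, and that is not valid censoring. It removes real events and can only lower the curve.

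The display matters because the protocol puts time to ADA forward as part of the evidence for biosimilarity. Protocol 5.2.1 also expects ADA to be examined against injection site reactions and loss of response, either of which could lead a patient to leave.

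**Working it through.** **Is there an overriding rule?** SAP 11.1 says only that time-to-event variables get Kaplan-Meier estimates and 95% CIs. SAP 11.4 says that immunogenicity data are not imputed. Neither gives an earlier positive result precedence over later discontinuation.

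**Documented inputs.** The documents state no ADA incidence, so there is no figure of the plan's own to reproduce. The only relevant number is dropout. At 20%, 260 × 0.80 = 208 remain at Week 52; the target of 200 tolerates 60/260 = 23.1%.

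**Illustration (assumed numbers).** Take 100 subjects, 40 of them first positive at Week 4. Later 20 leave, unrelated to ADA, so 0.20 × 40 = 8 of the leavers had been positive.
- Event kept: 40/100 = 40%.
- Literal rule: 32 events with 100 at risk at Week 4 = 32%.

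**Ceiling.** Let I be the 52-week incidence, d the proportion leaving and r the leaving risk of converters relative to non-converters. The share of converters who leave is L = r·d / (1 + (r − 1)·I). The literal rule keeps at least I·(1 − L), so the loss is at most I·L.
- r = 1, d = 0.20, I = 0.40: 0.40 × 0.20 = 8 points.
- r = 2, d = 0.20, I = 0.60: L = 0.40/1.60 = 0.25; 0.60 × 0.25 = 15 points.

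The actual loss is smaller because some would-be converters leave before turning positive.

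**Simulation (150,000 subjects per scenario).** Samples at Weeks 2, 4, 12, 24, 36 and 52; last sample 4 weeks after leaving. Assumptions not in the documents: incidence 10% to 60%; conversion early or at a constant hazard; leaving times uniform, or half of them at Week 24; r = 1 or 2. Week 52 Kaplan-Meier incidence in %, event kept → literal rule, at 20% leaving with uniform times (differences in points, taken before rounding):

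| Assumed incidence | Early, r = 1 | Early, r = 2 | Constant, r = 1 | Constant, r = 2 |
|---|---|---|---|---|
| 20% | 20.0 → 16.7 (3.3) | 19.7 → 14.2 (5.5) | 19.9 → 18.0 (1.9) | 18.4 → 15.1 (3.3) |
| 40% | 40.0 → 33.7 (6.3) | 39.0 → 30.0 (9.0) | 39.9 → 36.2 (3.7) | 37.5 → 32.2 (5.3) |
| 60% | 59.9 → 51.1 (8.8) | 58.9 → 47.8 (11.1) | 59.9 → 54.8 (5.0) | 57.7 → 51.1 (6.6) |

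Range over all scenarios, by study discontinuation:
- 23.1%: 1.0 to 13.6 points
- 20%: 1.0 to 11.7 points
- 10%: 0.5 to 5.7 points
- 5%: 0.2 to 2.8 points

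**Between arms.** A second simulation placed first positives at those six visits with weights 15, 25, 30, 15, 10 and 5%, with 20% leaving uniformly over Weeks 3 to 50. Give both arms a true incidence of 45%, with r = 1 in one and r = 2 in the other.
- Literal rule: 38.7% against 34.9%, a gap of 3.8 points.
- Event kept: 44.9% against 43.6%, a gap of 1.3 points, because leaving is itself informative.
- The wording therefore adds 3.8 − 1.3 = 2.5 points.

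For scale, the 95% half-width for a difference at 45% with 130 per arm is 1.96 × √(2 × 0.45 × 0.55 / 130) = 12.1 points.

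**The case against.** The strongest reply is that this is loose drafting. A subject with a positive sample has an observed event time, and most programmers would read the sentence as a list of ways in which follow-up can end without the event. The ACR20 rule shows that the authors know the standard convention. This stands as far as intent goes, and the bias appears only if the text is programmed literally. It does not rescue the sentence: on that reading the first two groups are redundant, and the text nowhere says that they must be event-free.

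Second, 20% may be too high for this purpose. It is a planning allowance, and the rule concerns leaving the study, not stopping treatment. Protocol 5.4.2 keeps patients withdrawn from IMP in immunogenicity follow-up to the end of the trial. This stands, and is why lower rates are shown. The boundary is not clean, though. Protocol 5.4.1 describes visits at 4 weeks and 4 months after the last dose. SAP section 8 cuts the final-analysis data of early terminators at theoretical Week 52 or the 4-month visit, whichever is first. A Week 24 non-responder last dosed at Week 22 could end near Week 40, and the documents do not say whether that counts as discontinuing the study.

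Third, other outputs are untouched: overall ADA status, titers, and the by-visit ADA and NAb counts do not use this rule. A curve that had lost events would also visibly disagree with the overall proportion positive. This stands.

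A reader might infer that the more immunogenic product would come out looking less immunogenic. The documents do not support that. They give no link between ADA and leaving. Similar leaving in both arms gives similar bias in both, and the overall incidence is unaffected. The between-arm effect is confined to one descriptive display and needs leaving after ADA to differ by arm.

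**Conclusion.** The point holds, conditionally. As written, the rule censors discontinuers and those lost to follow-up with no exception for an earlier positive result, contrary to the SAP's own definition of ADA positive and its time-to-ACR20 rule. Programmed literally, it lowers the Kaplan-Meier ADA incidence; every scenario run went in that direction.

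The size cannot be derived from the documents. It is about 1 to 12 points at 20% study discontinuation and under 3 points at 5%, given assumed incidence of 10% to 60%, early or constant conversion, and converters one to two times as likely to leave. A narrower range, such as 4 to 10 points, would be tempting to state as a finding. It would hold only for higher incidence, early conversion or excess leaving among converters, none of which is documented.

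The primary endpoint is not affected. The sentence should nevertheless be corrected, because it states a wrong rule for an analysis that the protocol assigns to the comparison of the products.

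**What to change.** Replace the censoring sentence in SAP 15.3.2 with:

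> The event is the date of the first positive post-dose ADA sample, regardless of any later discontinuation of treatment or study; only subjects with no positive post-dose ADA sample are censored, at the date of their last evaluable ADA sample.

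This also removes the need to decide who counts as having discontinued the study. The cost is one sentence in the SAP and a check that the program follows it; no new data are needed. If the programmers already intended this rule, the edit only records it.

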#### Immunogenicity

#### **Numbers of patients who develop ADA, the ADA titer, and numbers of patients who develop anti-adalimumab neutralizing antibodies**

An important objective of this clinical study is to investigate whether the CCI based formulation of MSB11022 displays a comparable immune response when compared to Humira®. The appearance of an immune response will be assessed in terms of formation of anti-drug-antibodies (ADA) and in terms of clinical manifestations.

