## 8.5 Description of Statistical Analyses

### 8.5.1 General Considerations

Full details of all planned analyses will be provided in the SAP, to be finalized and approved prior to database lock.

Baseline is defined as the day on which the first dose of the IMP (blinded trial drug) is administered.

Descriptive statistics will be given with reference to the analysis set deemed appropriate for each particular endpoint.

The following descriptive statistics will be used to summarize the trial data per treatment group on the basis of their nature unless otherwise specified:

- Continuous variables: n (number of non-missing observations), mean, standard deviation, 95% confidence interval (CI), median, minimum, and maximum
- Categorical variables: Frequencies and percentages
- Time to event variables: Kaplan-Meier estimates and 95% CIs

No correction for multiplicity is anticipated.

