11.1 Descriptive Methods

Descriptive statistics for continuous data will include the following:

- Number of subjects with non-missing data (n)
- Number of subjects with missing data
- Mean, standard deviation (SD)
- Median, first and third quartiles (Q1 and Q3)
- Minimum and maximum
- 95% confidence interval (CI).

All statistics will be rounded according to Merck's Global Biostatistics Output Standards (GBSOS) Booklet (Version 4.0 or later), ie, percentages will be rounded to one decimal. The mean, median, Q1, Q3, and 95% CI will be presented with one additional decimal compared to the raw data; SD will be presented with two additional decimals compared to the raw data; and minimum and maximum will be presented with the same number of decimals as the raw data.

All data will be presented by nominal visit (including the safety follow-up visits – four weeks and four months after the last dose of IMP) and no visit windowing rules will be implemented. Data from unscheduled visits will be listed but will not be included in summaries presented by

visit. The exceptions will be in the calculation of the baseline values. Data from unscheduled visits will also be included in the calculation of the worst on-treatment values and grades.

Categorical data will be summarized by presenting the number of subjects with non-missing data (n), the number of subjects with missing data (missing), and the number and percentage of subjects in each category. Percentages will be based on the number of subjects with non-missing data in the analysis set of interest, unless otherwise specified.

Time to event variables will be summarized by presenting Kaplan Meier estimates and 95% CIs.

Change from baseline will be calculated as the post-baseline value minus the baseline value. Percent change from baseline is defined as (100 x (post-baseline – baseline) / baseline).

If all baseline values are missing for a particular variable, the change from baseline and percent change/percent improvement from baseline will not be calculated.

A 2-sided significance level of 5% will be used for all analyses. Two-sided 95% confidence intervals will be calculated.

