15.2 Secondary Endpoint Analyses

15.2.1 Key Secondary Endpoint Analyses

The key secondary endpoint is ACR20 at Week 12.

The ACR20 is a key efficacy measure for which a subject must have at least 20% improvement from baseline in the following ACR Core Set values:

• TJC (68 joint count) and

- SJC (66 joint count) and
- An improvement of at least 20% from baseline in at least three of the following five assessments:
 - Patient's Global Assessment of Disease Activity on a visual analog scale (VAS)
 - Patient's Assessment of Arthritis Pain
 - Patient's Assessment of Physical Function as measured by the HAQ-DI
 - Physician's Global Assessment of Disease Activity
 - Acute phase reactant as measured by CRP.

The proportion of subjects with an ACR20 response at Week 12 in the two treatment arms will be reported along with Exact 95% CIs, calculated with the Clopper-Pearson method. The 95% CI for the difference between treatment arms in the proportion of subjects with an ACR20 response at Week 12, calculated with the Newcombe method, will also be presented.

The analyses will be carried out on both the ITT and the PP analysis sets.

Proportions for the two treatment arms will also be presented broken down by the subgroups for the ITT analysis set as described in Section 10.2.6.

Missing data will be handled as described in Section 11.4.1.

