15.3.2.1 Efficacy/ADA Correlation Analysis

Summary tables will present ACR20 and ACR50 by ADA status. A line graph will also be provided to display the ACR20 response rate over time by treatment arm and ADA status.

Boxplots displaying *DAS28-ESR* change from baseline at Week 12 by both ADA status and lower and upper quartiles of ADA titers will be produced. The change from baseline for *DAS28-ESR* will be the value for the specified visit, the ADA status or ADA titers will be the values for the treatment period.

The ADA titer quartiles will be defined using the highest ADA titer value from each subject for the period from baseline to Week 12 where subjects with ADA negative for the whole period will be assigned to a titer value of 0. ADA titers will be computed by splitting the subjects by treatment arm, taking their highest ADA titer values for the treatment period, arranging the values from smallest to largest and splitting into quartiles.

Line graphs will also be provided to display the change from baseline over time for continuous efficacy endpoints (TJC28, SJC28, ESR, DAS28-ESR, CDAI, SDAI), split by treatment arm and ADA status at a specified visit.

In addition, scatterplots of percentage change from baseline in continuous efficacy endpoints (DAS28-ESR, CDAI, SDAI) vs titer on log2 scale (if appropriate) will be generated for each treatment with separate symbols (if appropriate) for each study week.

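### The SAP names no confidence interval for the ADA and NAb percentages or their between-arm difference, and summarises titers on the raw scale with no geometric mean

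*SAP*

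**What the plan says.** **Titers.** SAP 15.3.2: "Summary statistics will be presented for the actual titer values, by treatment arm and visit up to Week 52". It names no statistics, so the general default applies. The SAP 11.1 list for continuous data has n, missing, mean, SD, median, quartiles, range and a 95% CI whose method is not given. Protocol 8.5.1 is similar: "Continuous variables: n (number of non-missing observations), mean, standard deviation, 95% confidence interval (CI), median, minimum, and maximum". Boxplots of the quartiles, median and range are also planned. A log2 scale for titer appears only for scatterplots in SAP 15.3.2.1, and there only where appropriate.

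**Positivity.** SAP 15.3.2: "The number and percentage of ADA positive and NAb positive subjects will be presented for each visit up to Week 52". Overall ADA status and presence of NAb are summarised too. The SAP 11.1 default for categorical data is counts and percentages. Protocol 8.5.3.5 also asks for number and percentage.

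**Intervals that are planned for immunogenicity.** SAP 15.3.2 analyses time to positive ADA status by Kaplan-Meier, with a median, a 95% CI and numbers at risk. SAP 11.1 adds a general sentence that two-sided 95% CIs will be calculated, tied to no endpoint or method.

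**Elsewhere in the SAP.** For ACR20, section 15.2.1 gives Clopper-Pearson intervals per arm, and the interval for the difference, "calculated with the Newcombe method, will also be presented". Section 15.1 gives AESIs Clopper-Pearson intervals and the half-width for the arm difference. Section 15.3.3.1 gives PK concentrations a geometric mean and geometric CV.

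**The concern.** Immunogenicity is in the trial title and has its own comparative secondary objective (Protocol 4.2.2). Protocol 5.2.3.3 calls it an important objective to learn whether the new formulation "displays a comparable immune response when compared to Humira". A comparative objective needs some measure of how precisely the two arms are compared. The SAP supplies one for ACR20 and for the AESIs, but not for the ADA and NAb percentages. A reader shown two percentages could take a gap of several points as a difference, or a small gap as evidence of similarity, without seeing what the data can resolve.

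The titer issue is separate. Titers come from serial dilution and tend to spread multiplicatively, so a few very high values can dominate an arithmetic mean. A symmetric interval around that mean may then miss its nominal coverage, and may even extend below zero. How far this matters depends on the spread.

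**Working it through.** **1. The plan's own precision figure.** The only one is for AESIs (Protocol 8.1, SAP 7.1): 12.0% and 9.0% at incidences of 26.0% and 11.0%. The half-width for a difference of two equal proportions is 1.96 × √(2p(1−p)/n). With n = 100 per arm:
- p = 0.26: 1.96 × √(2 × 0.26 × 0.74 / 100) = 12.2%
- p = 0.11: 1.96 × √(2 × 0.11 × 0.89 / 100) = 8.7%

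These match the stated figures to whole percents. So the plan already thinks in terms of precision of the arm difference at about 100 per arm. It gives no such figure for ADA or NAb.

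**2. What the missing intervals would be.** Inputs: 130 per arm randomised and about 100 per arm at Week 52 (Protocol 8.1). ADA incidence is not given in the documents, so 20%, 30% and 50% are assumed, equal in both arms. With equal proportions p and Wilson limits l and u, the Newcombe half-width is √((p−l)² + (u−p)²). Example at 26/130: l = 0.1403, u = 0.2769, so √(0.0597² + 0.0769²) = 0.097.

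| Incidence | Clopper-Pearson, n = 130 | Newcombe, n = 130 | Clopper-Pearson, n = 100 | Newcombe, n = 100 |
|---|---|---|---|---|
| 20% | 13.5-27.9% | ±9.7 points | 12.7-29.2% | ±11.1 points |
| 30% | 22.3-38.7% | ±11.0 points | 21.2-40.0% | ±12.6 points |
| 50% | 41.1-58.9% | ±12.0 points | 39.8-60.2% | ±13.6 points |

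**3. Coverage of the raw-mean titer interval.** The documents give no titer distribution, dilution scheme or number of positives. Assumptions: log-normal titers, SD of log2 titer 1, 2 or 3, and 25, 40 or 60 positives per arm. The interval is mean ± t × SD/√n on the raw scale, the usual reading of an unnamed CI for a mean. Results are from 200,000 simulated samples per cell.

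| log2 SD | Coverage, n = 25 / 40 / 60 | Lower limit below zero |
|---|---|---|
| 1 | 92 / 93 / 93% | 0 / 0 / 0% |
| 2 | 80 / 83 / 85% | 7 / 3 / 1% |
| 3 | 62 / 66 / 68% | 37 / 25 / 17% |

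The t interval on the log scale, back-transformed to the geometric mean titer, covers 95% in every cell. Rounding titers to two-fold steps changes raw-mean coverage by no more than about 2 points.

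**4. ADA-negative subjects.** SAP 15.3.2.1 scores them zero for the quartile analysis; 15.3.2 does not say whether they enter the by-visit titer summary. If they enter as zeros, with 100 per arm and 10-80% positive, raw-mean coverage is 89-94% at log2 SD 1, 74-87% at 2 and 53-71% at 3.

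**The case against.** The strongest reply is that the descriptive approach is deliberate. Protocol 5.2.1 says regulators favour a full but descriptive presentation of immunogenicity and that the study cannot be powered for equivalence on it. There is no margin, test or decision rule, and anyone with the counts can compute an interval. That stands as an argument against a formal test. It does not argue against intervals: the guidance quoted in the same section, though written about safety, recommends adding them to descriptive summaries where they help interpretation.

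A reader might infer that immunogenicity gets no error bars at all. The documents do not support that. Kaplan-Meier time to ADA carries a 95% CI, and its complement is the cumulative ADA incidence in each arm. Titers also get medians, quartiles and boxplots, which extreme values do not distort in the same way. What these leave out is NAb and the difference between arms. In addition, the Kaplan-Meier median may not be reached if fewer than half the subjects turn positive.

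A reader might also infer that the titer intervals are known to be wrong. The documents give no spread, and at log2 SD 1 the loss is only 2 to 3 points. Nor does the word actual in 15.3.2 show a deliberate choice of the raw scale: in SAP 15.2.2.3 to 15.2.2.6 it marks observed values as against change from baseline. What remains is that no transformation or geometric mean is specified.

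Finally, comparing titers among ADA-positive subjects compares subsets formed after randomisation. That is correct, and the change below has to carry the caution.

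**Conclusion.** The point holds as a gap in presentation for a comparative secondary objective, and it should be closed.

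- **Percentages.** No interval is specified for ADA or NAb positivity, per arm or for the difference. The general CI sentence in SAP 11.1 does not fill this, since it names neither endpoint nor method. The unreported uncertainty in the difference is roughly 10 to 14 percentage points either way, at equal incidence of 20-50% with 100 to 130 subjects per arm. The incidences are assumed.
- **Titers.** The default gives a raw-scale mean and CI, with no geometric mean. Its undercoverage runs from slight to severe depending on a spread that the documents do not state; it rests on the log-normal assumption and is not an established fact.

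The primary endpoint, the key secondary endpoint and the sample size are untouched.

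**What to change.** In SAP 15.3.2:

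1. For ADA-ever-positive and NAb-ever-positive subjects in the Safety Analysis Set, add a Clopper-Pearson 95% CI per arm and the Newcombe 95% CI for the difference. State the denominator.
2. Replace the raw-mean CI for titers with the geometric mean titer and a log-scale 95% CI among ADA-positive subjects, using one value per subject per visit so that repeated samples are not pooled as if independent. Keep the median and quartiles, and draw the boxplots on a log2 axis.
3. State that ADA-negative subjects are excluded from this titer summary.
4. If a between-arm geometric mean ratio is shown, label it descriptive and note that ADA-positive subjects are a subset defined after randomisation.

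The cost is some SAP wording and a few more outputs, with interval methods the SAP already uses for ACR20. No new data are needed, and the analysis stays descriptive with no test or margin. The wording should be settled before database lock and unblinding.
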